Appendix 7. I1F-MC-RHCG Blood Volume Prioritization Tool

Due to blood volume restrictions, some laboratory samples may not be collected.

This appendix (Blood Volume Prioritization Tool) provides guidance on blood sample prioritization for participants who will participate in the study. This tool includes a separate table for each of the following age groups:

- 15 years and older (page 173-174)
- 8 years to <15 years (page 175-176)
- 2 years to <8 years (page 177-178)
- Blood volume calculations (page 179)

Blood Volume Prioritization Recommendations for Participants ages 15 yrs and older															
Laboratory Test (all tests per protocol)	V1	V2	V3	V4	V5	V6	V7	V8	V11	V14	V17	V20	V23	V26	V29
Chemistry/hs-CRP (includes serum B-HCG, Rheumatoid Factor at screening)	4.7	4.7		4.7			4.7		4.7	4.7	4.7	4.7	4.7	4.7	4.7
Hematology (w/ANC)	1.2	1.2		1.2			1.2		1.2	1.2	1.2	1.2	1.2	1.2	1.2
Flow Cytometry		4.9					4.9		4.9	4.9	4.9	4.9	4.9	4.9	4.9
Hepatitis B/C Initial Screening	4.7														
HIV Screening/Confirmation	1.1														
TB Quantiferon (4 mL) or PPD Test (if applicable)	4.0														
HBV DNA Reflex Confirmation (separate day, 4.9 mL)	X														
HCV RNA Reflex Confirmation (separate day, 4.9 mL)															
HBV DNA monitoring - (4.9 mL, if applicable)	X					X			X	X	X		X	X	X
hs-CRP (V3, V5, V6, V8 only, otherwise with chem)			1.1		1.1	1.1		1.1							
Rheumatoid Factor (with Chem)															
HLA-B27				2.7											
ESR		1.5	1.5	1.5	1.5	1.5	1.5	1.5	1.5	1.5	1.5	1.5	1.5	1.5	1.5
PK Sample (to be collected for patients on active LY)		2.6		2.6		2.6	2.6	2.6	2.6		2.6		2.6		2.6
Immunogenicity (ADA and Nab)		4.7		4.7		4.7	4.7	4.7	4.7		4.7		4.7		4.7
Actual Blood Volume by Visit (mL)	15.7	19.6	2.6	17.4	2.6	9.9	19.6	9.9	19.6	12.3	19.6	12.3	19.6	12.3	19.6

Abbreviations: ADA = antidrug antibody; ANC = absolute neutrophil count; B-HCG = Beta-Human Chorionic Gonadotropin; Chem = Chemistry; ESR = erythrocyte sedimentation rate; HBV = hepatitis B virus; HCV = hepatitis C virus; HIV = human immunodeficiency virus; HLA-B27 = human leukocyte antigen-B27; hs-CRP = high sensitivity C-reactive protein; Nab = neutralizing antidrug antibody; PK = pharmacokinetic; PPD = purified protein derivative; TB = tuberculosis; V = visit.

Blood Volume Prioritization																			
Recommendations for Participants ages 15 yrs and older																			
Laboratory Test (all tests per protocol)	V30	V31	V33	V36	V39	V42	V45	V48	V51	V54	V57	V60	V63	V66	V69	ET	V801	V802	V803
Chemistry/hs-CRP (includes serum B-HCG, Rheumatoid Factor at screening)	4.7		4.7	4.7	4.7	4.7	4.7	4.7	4.7	4.7	4.7	4.7	4.7	4.7	4.7	4.7	1.1	1.1	1.1
Hematology (w/ANC)	1.2		1.2	1.2	1.2	1.2	1.2	1.2	1.2	1.2	1.2	1.2	1.2	1.2	1.2	1.2	1.2	1.2	1.2
Flow Cytometry																			
Hepatitis B/C Initial Screening (with Chem)																			
HIV Screening/Confirmation																			
TB Quantiferon (4 mL) or PPD Test (if applicable)																			
HBV DNA Reflex Confirmation (separate day, 4.9 mL) HCV RNA Reflex Confirmation (separate day, 4.9 mL)	X																		
HBV DNA monitoring - (4.9 mL, if applicable)	X		X	X	X	X	X	X	X	X	X	X	X	X	X		X		
hs-CRP (V3, V5, V6, V8 only, otherwise with chem)																			
Rheumatoid Factor (with Chem)																			
HLA-B27																			
ESR	1.5		1.5	1.5	1.5	1.5	1.5	1.5	1.5	1.5	1.5	1.5	1.5	1.5	1.5	1.5			
PK Sample (to be collected for patients on active LY)	2.6	2.6	2.6	2.6		2.6		2.6		2.6		2.6		2.6	2.6	2.6		2.6	
Immunogenicity (ADA and Nab)	4.7	4.7	4.7	4.7		4.7		4.7		4.7		4.7		4.7	4.7	4.7		4.7	
Actual Blood Volume by Visit (mL)	14.7	7.3	14.7	14.7	7.4	14.7	7.4	14.7	7.4	14.7	7.4	14.7	7.4	14.7	14.7	14.7	2.3	9.6	2.3

Abbreviations: ADA = antidrug antibody; ANC = absolute neutrophil count; B-HCG = Beta-Human Chorionic Gonadotropin; Chem = chemistry; ESR = erythrocyte sedimentation rate; ET = early termination; HBV = hepatitis B virus; HCV = hepatitis C virus; HIV = human immunodeficiency virus; HLA-

B27 = human leukocyte antigen-B27; hs-CRP = high sensitivity C-reactive protein; Nab = neutralizing antidrug antibody; PK = pharmacokinetic; PPD = purified protein derivative; TB = tuberculosis; V = visit.

Blood Volume Prioritization															
Recommendations for Participants age 8 to < 15 yrs															
Laboratory Test (all tests per protocol)	V1	V2	V3	V4	V5	V6	V7	V8	V11	V14	V17	V20	V23	V26	V29
Chemistry/hs-CRP (includes serum B-HCG, Rheumatoid Factor at screening)	4.7	4.7		4.7			4.7		4.7	4.7	4.7	4.7	4.7	4.7	4.7
Hematology (w/ANC)	1.2	1.2		1.2			1.2		1.2	1.2	1.2	1.2	1.2	1.2	1.2
Flow Cytometry		4.9					4.9		4.9	4.9	4.9	4.9	4.9	4.9	4.9
Hepatitis B/C Initial Screening	4.7														
HIV Screening/Confirmation	1.1														
TB Quantiferon (4 mL) or PPD Test (if applicable)	4.0														
HBV DNA Reflex Confirmation (separate day, 4.9 mL) HCV RNA Reflex Confirmation (separate day, 4.9 mL)	X														
HBV DNA monitoring, if applicable (separate day, 4.9mL)	X						X		X	X	X		X	X	X
hs-CRP (V3, V5, V6, V8 only, otherwise with chem)			1.1		1.1	1.1		1.1							
Rheumatoid Factor (with Chem)															
HLA-B27				2.7											
ESR		1.5	1.5	1.5	1.5	1.5	1.5	1.5	1.5	1.5	1.5	1.5	1.5	1.5	1.5
PK Sample (to be collected for patients on active LY)		2.6		2.6		2.6	2.6	2.6		2.6		2.6		2.6	2.6
Immunogenicity (ADA and Nab)		4.7		4.7		4.7	4.7	4.7		4.7		4.7		4.7	4.7
Actual Blood Volume by Visit (mL)	15.7	19.6	2.6	17.4	2.6	9.9	19.6	9.9	19.6	12.3	19.6	12.3	19.6	12.3	19.6

Abbreviations: ADA = antidrug antibody; ANC = absolute neutrophil count; B-HCG = Beta-Human Chorionic Gonadotropin; Chem = Chemistry; ESR = erythrocyte sedimentation rate; HBV = hepatitis B virus; HCV = hepatitis C virus; HIV = human immunodeficiency virus; HLA-B27 = human leukocyte antigen-B27; hs-CRP = high sensitivity C-reactive protein; Nab = neutralizing antidrug antibody; PK = pharmacokinetic; PPD = purified protein derivative; TB = tuberculosis; V = visit.

Blood Volume Prioritization Recommendations for Participants age 8 to < 15 yrs																			
Laboratory Test (all tests per protocol)	V30	V31	V33	V36	V39	V42	V45	V48	V51	V54	V57	V60	V63	V66	V69	ET	V801	V802	V803
Chemistry/hs-CRP (includes serum B-HCG, Rheumatoid Factor at screening)	4.7		4.7	4.7	4.7	4.7	4.7	4.7	4.7	4.7	4.7	4.7	4.7	4.7	4.7	4.7	1.1	1.1	1.1
Hematology (w/ANC)	1.2		1.2	1.2	1.2	1.2	1.2	1.2	1.2	1.2	1.2	1.2	1.2	1.2	1.2	1.2	1.2	1.2	1.2
Flow Cytometry																			
Hepatitis B/C Initial Screening (with Chem)																			
HIV Screening/Confirmation																			
TB Quantiferon (4 mL) or PPD Test (if applicable)																			
HBV DNA Reflex Confirmation (separate day, 4.9 mL) HCV RNA Reflex Confirmation (separate day, 4.9 mL)	X																		
HBV DNA monitoring, if applicable (separate day, 4.9mL)	X		X	X	X	X	X	X	X	X	X	X	X	X	X	X		X	
hs-CRP (V3, V5, V6, V8 only, otherwise with chem)																			
Rheumatoid Factor (with Chem)																			
HLA-B27																			
ESR	1.5		1.5	1.5	1.5	1.5	1.5	1.5	1.5	1.5	1.5	1.5	1.5	1.5	1.5	1.5			
PK Sample (to be collected for patients on active LY)	2.6	2.6	2.6	2.6		2.6		2.6		2.6		2.6		2.6	2.6	2.6	2.6		
Immunogenicity (ADA and Nab)	4.7	4.7	4.7	4.7		4.7		4.7		4.7		4.7		4.7	4.7	4.7	4.7		
Actual Blood Volume by Visit (mL)	14.7	7.3	14.7	14.7	7.4	14.7	14.7	14.7	2.3	9.6	2.3								

Abbreviations: ADA = antidrug antibody; ANC = absolute neutrophil count; B-HCG = Beta-Human Chorionic Gonadotropin; Chem = Chemistry; ESR = erythrocyte sedimentation rate; ET = early termination; HBV = hepatitis B virus; HCV = hepatitis C virus; HIV = human immunodeficiency virus; HLA-B27 = human leukocyte antigen-B27; hs-CRP = high sensitivity C-reactive protein; Nab = neutralizing antidrug antibody; PK = pharmacokinetic; PPD = purified protein derivative; TB = tuberculosis; V = visit.

Blood Volume Prioritization															
Recommendations for Participants age 2 to < 8 yrs															
Laboratory Test (all tests per protocol)	V1	V2	V3	V4	V5	V6	V7	V8	V11	V14	V17	V20	V23	V26	V29
Chemistry/hs-CRP (includes serum B-HCG, Rheumatoid Factor at screening)	4.7	4.7		4.7			4.7		4.7	4.7	4.7	4.7	4.7	4.7	4.7
Hematology (w/ANC)	1.2	1.2		1.2			1.2		1.2	1.2	1.2	1.2	1.2	1.2	1.2
Flow Cytometry (if eligible)		X					X		X	X	X	X	X	X	X
Hepatitis B/C Initial Screening	4.7														
HIV Screening/Confirmation	1.1														
PPD Test (if applicable)															
HBV DNA Reflex Confirmation (separate day, 4.9 mL)	X														
HCV RNA Reflex Confirmation (separate day, 4.9 mL)															
HBV DNA monitoring, if applicable (separate day, 4.9mL)	X					X			X	X	X		X	X	X
hs-CRP (V3, V5, V6, V8 only, otherwise with chem)			1.1		1.1	1.1		1.1							
Rheumatoid Factor (with Chem)															
HLA-B27				2.7											
ESR		1.5	1.5	1.5	1.5	1.5	1.5	1.5	1.5	1.5	1.5	1.5	1.5	1.5	1.5
PK Sample (to be collected for patients on active LY)		2.6		2.6		2.6	2.6	2.6	2.6	2.6	2.6	2.6	2.6	2.6	2.6
Immunogenicity (ADA and Nab)		4.7		4.7		4.7	4.7	4.7	4.7	4.7	4.7	4.7	4.7	4.7	4.7
Actual Blood Volume by Visit (mL)	11.7	14.7	2.6	17.4	2.6	9.9	14.7	9.9	14.7	7.4	14.7	7.4	14.7	7.4	14.7

Abbreviations: ADA = antidrug antibody; ANC = absolute neutrophil count; B-HCG = Beta-Human Chorionic Gonadotropin; Chem = Chemistry; ESR = erythrocyte sedimentation rate; HBV = hepatitis B virus; HCV = hepatitis C virus; HIV = human immunodeficiency virus; HLA-B27 = human leukocyte antigen-B27; hs-CRP = high sensitivity C-reactive protein; Nab = neutralizing antidrug antibody; PK = pharmacokinetic; PPD = purified protein derivative; V = visit.

Blood Volume Prioritization Recommendations for Participants age 2 to < 8 yrs																			
Laboratory Test (all tests per protocol)	V30	V31	V33	V36	V39	V42	V45	V48	V51	V54	V57	V60	V63	V66	V69	ET	V801	V802	V803
Chemistry/hs-CRP (includes serum B-HCG, Rheumatoid Factor at screening)	4.7		4.7	4.7	4.7	4.7	4.7	4.7	4.7	4.7	4.7	4.7	4.7	4.7	4.7	4.7	1.1	1.1	1.1
Hematology (w/ANC)	1.2		1.2	1.2	1.2	1.2	1.2	1.2	1.2	1.2	1.2	1.2	1.2	1.2	1.2	1.2	1.2	1.2	1.2
Flow Cytometry (if eligible)																			
Hepatitis B/C Initial Screening (with Chem)																			
HIV Screening/Confirmation																			
PPD Test (if applicable)																			
HBV DNA Reflex Confirmation (separate day, 4.9 mL)	X																		
HCV RNA Reflex Confirmation (separate day, 4.9 mL)																			
HBV DNA monitoring, if applicable (separate day, 4.9mL)	X		X	X	X	X	X	X	X	X	X	X	X	X	X	X	X	X	
hs-CRP (V3, V5, V6, V8 only, otherwise with chem)																			
Rheumatoid Factor (with Chem)																			
HLA-B27																			
ESR	1.5		1.5	1.5	1.5	1.5	1.5	1.5	1.5	1.5	1.5	1.5	1.5	1.5	1.5	1.5	1.5	1.5	
PK Sample (to be collected for patients on active LY)	2.6	2.6	2.6	2.6		2.6		2.6		2.6		2.6		2.6		2.6	2.6	2.6	
Immunogenicity (ADA and Nab)	4.7	4.7	4.7	4.7		4.7		4.7		4.7		4.7		4.7		4.7	4.7	4.7	
Actual Blood Volume by Visit (mL)	14.7	7.3	14.7	14.7	7.4	14.7	14.7	14.7	2.3	9.6	2.3								

Abbreviations: ADA = antidrug antibody; ANC = absolute neutrophil count; B-HCG = Beta-Human Chorionic Gonadotropin; Chem = Chemistry; ESR = erythrocyte sedimentation rate; ET = early termination; HBV = hepatitis B virus; HCV = hepatitis C virus; HIV = human immunodeficiency virus; HLA-B27 = human leukocyte antigen-B27; hs-CRP = high sensitivity C-reactive protein; Nab = neutralizing antidrug antibody; PK = pharmacokinetic; PPD = purified protein derivative; V = visit.

Blood Volume Prioritization

Blood Volume Calculations

Blood Volume Calculations

- Local restrictions may apply with regard to allowed volume of samples within 24 hours.
- Please ensure that you are compliant with local restrictions as applicable.

Conservative guidance is:

1% of total blood volume for age and weight per 24 hours

Conservative estimate of total blood volume is 80 mL/kg

15 years or older (and $\geq 40\text{kg}$) $\rightarrow (80\text{mL/kg} \times 40\text{kg})/100 = 32\text{mL per 24 hours}$
15 year old 5th percentile of weight is 40kg (CDC)

8 to <15 years (and 20 to <40kg) $\rightarrow (80\text{mL/kg} \times 20\text{kg})/100 = 16\text{mL per 24 hours}$
8 year old 5th percentile of weight is 20kg (WHO)

6 to <8 years (and 15 to <20kg) $\rightarrow (80\text{mL} \times 15\text{kg})/100 = 12\text{mL per 24 hours}$
6 year old 5th percentile of weight is 16kg (WHO)

2 to <6 years (and 10 to <15kg) $\rightarrow (80\text{mL} \times 10\text{kg})/100 = 8\text{mL per 24 hours}$
2 year old 5th percentile of weight is 10kg (CDC)

Abbreviations: CDC = Centers for Disease Control; WHO = World Health Organization.

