9.4.4. Laboratory Tests

For each participant, laboratory tests detailed in [Appendix 2](#) should be conducted according to the Schedule of Activities (Section 2).

Blood volume restrictions are anticipated to be applicable for participants 2 to <8 years old and particularly for participants 10.0 to <20.0 kg in body weight; however, it may be used for older participants if local regulations require restrictions on blood volumes. The Blood Volume Prioritization Tool is provided in [Appendix 7](#).

Due to blood volume restrictions, some laboratory samples may not be collected (for example, cell flow cytometry in case needed to reduce blood volumes of a certain visit). Laboratory samples should be collected as described in a sponsor-provided weight-based prioritization chart.

Additional allowances to accommodate blood volume restrictions may include, but are not limited to the following:

- Blood draws for Visit 1 and Visit 2 may be divided over 2 days if the 24-hour blood volume limit is exceeded.
- Hepatitis B virus DNA will be collected as a reflex test prior to Visit 2 and is only required for participants who are positive for HBcAb.
- Hepatitis C virus RNA will be collected as a reflex test prior to Visit 2 and is only required for participants who are positive for HCV antibody.

Use of local anesthetics or devices consistent with local prescribing information is permitted during the study visit to ease discomfort associated with venipunctures. Lilly or its designee will provide the investigator with the results of laboratory tests analyzed by a central vendor, if a central vendor is used for the clinical study.

Any clinically significant findings from laboratory tests that result in a diagnosis and that occur after the participant receives the first dose of investigational product should be reported to Lilly or its designee as AE via electronic data entry.

The investigator must review the laboratory report, document this review, and record any clinically relevant changes occurring during the study in the AE section of the CRF. The laboratory reports must be filed with the source documents.

9.4.5. *Pregnancy Testing*

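### Appendix 7's table for ages 2 to <8 lists visit totals above the appendix's own conservative 24-hour figures of 8 and 12 mL, and the reliefs the protocol names do not close the gap

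*Protocol*

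**What the plan says.** The last page of Protocol Appendix 7 gives conservative guidance of "1% of total blood volume for age and weight per 24 hours", taking blood volume as 80 mL/kg. It works out one figure per band from the band's lowest weight. The line beginning "2 to <6 years (and 10 to <15kg" arrives at 8 mL, and the line beginning "6 to <8 years (and 15 to <20kg" arrives at 12 mL. The same page defers to local rules: "Please ensure that you are compliant with local restrictions as applicable".

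One table, headed "Recommendations for Participants age 2 to < 8 yrs", serves both bands. It is already trimmed in three ways. Flow cytometry carries no volume, QuantiFERON is not listed, and hepatitis confirmation and monitoring go elsewhere ("HBV DNA monitoring, if applicable (separate day, 4.9mL").

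Protocol 9.4.4 expects restrictions at 2 to <8 years, above all at 10 to <20 kg. It lets sites leave samples out, with flow cytometry as its example, and points to a sponsor-provided chart based on weight. Its list of further measures opens "Additional allowances to accommodate blood volume restrictions may include, but are not limited to the following". The only item on that list that divides routine tubes reads "Blood draws for Visit 1 and Visit 2 may be divided over 2 days if the 24-hour blood volume limit is exceeded".

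**The concern.** Two parts of one appendix disagree. A site that draws the column as listed goes over the appendix's own figure in the lightest children. A site that cuts to the figure finds no order of priority in Appendix 7, although the appendix is presented as a prioritization tool. At stake are the blood taken from small children relative to the sponsor's own guidance, and whether sites sacrifice the same tubes. Ixekizumab trough concentration and anti-ixekizumab antibody status are both secondary endpoints (Protocol Section 4).

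**Working it through.** **Inputs.** Tube volumes in mL from the Appendix 7 table for ages 2 to <8: chemistry/hsCRP 4.7; hematology 1.2; ESR 1.5; PK 2.6 (children on ixekizumab only); immunogenicity 4.7; HLA-B27 2.7; hsCRP alone 1.1; hepatitis screen 4.7; HIV 1.1.

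**Limits reproduced.** 80 × weight / 100 gives 8 mL at 10 kg and 12 mL at 15 kg, as stated. The weight at which a volume equals 1% is volume / 0.8.

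**Totals reproduced.** Every listed total through Week 104 matches the sum of its tubes.

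| Visits | Sum (mL) | Over 8? | Over 12? | Within 1% from |
|---|---|---|---|---|
| V1 | 4.7 + 1.2 + 4.7 + 1.1 = 11.7 | yes | no | 14.6 kg |
| V2, V7, V11, V17, V23, V29 | 4.7 + 1.2 + 1.5 + 2.6 + 4.7 = 14.7 | yes | yes | 18.4 kg |
| V4 | 14.7 + 2.7 = 17.4 | yes | yes | 21.75 kg |
| V6, V8 | 1.1 + 1.5 + 2.6 + 4.7 = 9.9 | yes | no | 12.4 kg |
| V14, V20, V26 | 4.7 + 1.2 + 1.5 = 7.4 | no | no | 9.25 kg |
| V3, V5 | 1.1 + 1.5 = 2.6 | no | no | 3.25 kg |

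**Count, child on ixekizumab.** Of 15 visits, 1 + 6 + 1 + 2 = 10 exceed 8 mL and 6 + 1 = 7 exceed 12 mL. The 14.7 mL total is 14.7/8 = 1.84 times the lower figure and 14.7/12 = 1.23 times the upper. At V4 the ratios are 17.4/8 = 2.18 and 17.4/12 = 1.45.

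**Count, child on adalimumab (no PK tube).** The larger visits fall to 14.7 − 2.6 = 12.1 mL, and V6 and V8 to 9.9 − 2.6 = 7.3 mL. Eight visits then exceed 8 mL.

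**Named reliefs.** Omitting flow cytometry changes nothing, because it has no volume in the table. Splitting V1 (5.9 + 5.8) and V2 (7.4 + 7.3) brings each day under 8 mL. V4, V6, V7, V8, V11, V17, V23 and V29 (8 visits) stay over 8 mL. V4, V7, V11, V17, V23 and V29 (6 visits) stay over 12 mL. A past HLA-B27 result takes V4 to 14.7 mL, still over both figures.

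**What fits.**
- Without immunogenicity, a 14.7 mL visit is 14.7 − 4.7 = 10.0 mL, which meets 12 mL and meets 1% of actual weight from 12.5 kg.
- Without immunogenicity and PK it is 7.4 mL, which meets 8 mL.
- V6 and V8 without PK are 7.3 mL. PK plus immunogenicity alone is also 2.6 + 4.7 = 7.3 mL.

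**Antibody evaluability.** SAP 6.12.12.1.2 requires a baseline sample and at least one post-baseline sample, or, with no baseline sample, post-baseline samples that are all negative. With the V2 split already allowed, and immunogenicity kept at V6 or V8 within 7.3 mL, a 10 kg child is evaluable with no extra draw day after V2.

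**The case against.** The strongest reply is that nothing here obliges anyone to overdraw. The 1% rule is called conservative guidance, and local limits take precedence. Omission is permitted in the Schedule of Activities, 5.1.1, 9.4.4 and Appendix 7 itself, and the 9.4.4 list is expressly open-ended. The table can be read as an inventory of protocol tests to set against a limit. The 8 and 12 mL figures are band floors, and a child gains weight over two years. ERA requires age 6 or older, so the 2 to <6 band contains JPsA only. The weight-based chart may be a separate document that ranks the tubes; Appendix 7's own tables are by age.

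All of that stands, and it limits the point to Appendix 7 and 9.4.4. It does not reconcile the two sets of numbers. The 14.7 mL total breaks the 1% rule across the whole 10 to <15 kg band, and 17.4 mL breaks it across both bands.

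A reader might infer that the plan forces excessive draws, or that primary-endpoint, PK or antibody data in small children will be lost. The documents support neither. The only blood tube in the JIA ACR core set is ESR, at 1.5 mL. At 10 kg, hsCRP, hematology, ESR and PK total 1.1 + 1.2 + 1.5 + 2.6 = 6.4 mL if full chemistry is given up. Antibody evaluability can be kept as shown above.

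**Conclusion.** The mismatch is real and exact. In the table for ages 2 to <8, 10 of 15 visits exceed the 8 mL figure and 7 of 15 exceed the 12 mL figure for a child on ixekizumab. After the splits the protocol names, 8 and 6 visits remain over. This assumes that the tubes are drawn as listed, that there is no past HLA-B27 result at V4, and that the band-floor figures apply. By actual weight, the 14.7 mL visits comply from 18.4 kg. Long-term extension visits were not counted, and the documents do not say how many children this young or light will enrol. It would go too far to say that the trial has no ranking of tubes: Appendix 7 has none, but the chart cited in 9.4.4 was not supplied. Severity is minor to should-fix.

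**What to change.** 1. Split the 2 to <8 table by weight band so that each same-day total meets the stated figure, or cite the ranked chart if it exists. Say whether 8 mL or 1% of actual weight applies from 12.5 to <15 kg.
2. Where no past HLA-B27 result exists, move that tube from V4 to V3 or V5 (2.6 + 2.7 = 5.3 mL). V4 falls to 14.7 mL, which also brings it under the 16 mL figure for ages 8 to <15.
3. Change 9.4.4 so that draws at any visit may optionally be divided over two days. Keep this optional, because Section 9 asks sites to consolidate draws.
4. In the 12 mL band, omit or defer immunogenicity at the 14.7 mL post-baseline visits (leaving 10.0 mL) and keep it at V6 and V8 (9.9 mL). If it is deferred, move PK with it, since 9.6.1 pairs the two.
5. Below 12.5 kg, take chemistry/hsCRP, hematology and ESR (7.4 mL) at the larger visits. Keep immunogenicity at V6 and V8 by omitting PK (7.3 mL). At V6, PK plus immunogenicity alone (7.3 mL) is an alternative, with ESR carried forward within the OLT period. SAP Appendix 1 bars carrying values across periods, so this does not extend to V8. Use the V2 split to keep the baseline antibody sample.

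The cost is an amendment to Appendix 7, one sentence in 9.4.4 and a Schedule of Activities edit for HLA-B27. Up to 6 of the 8 post-baseline immunogenicity samples through Week 104 are given up in the affected children, and below 12.5 kg PK samples at the larger visits as well. Where PK is omitted at V6 or V8, the antibody result lacks its paired concentration. Design, endpoints and sample size are unchanged.

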Appendix 8. Provisions for Changes in Study Conduct During Exceptional Circumstances

Implementation of this Appendix

The changes to procedures described in this appendix are temporary measures intended to be used only during specific time periods as directed by the sponsor in partnership with the investigator.

Exceptional Circumstances

Exceptional circumstances are rare events that may cause disruptions to the conduct of the study. Examples include pandemics or natural disasters. These disruptions may limit the ability of the investigators, participants, or both to attend on-site visits or to conduct planned study procedures.

Implementing Changes under Exceptional Circumstances

In an exceptional circumstance, after receiving the sponsor's written approval, sites may implement changes if permitted by local regulations.

After approval by local Ethical Review Boards, regulatory bodies, and any other relevant local authorities, implementation of these exceptional circumstance changes will not typically require additional notification to these groups, unless they have specific conditions in which notification is required. To protect the safety of study participants, urgent changes may be implemented before approval but need to be reported as soon as possible. All approvals must be retained in the study records.

If the sponsor grants written approval for changes in study conduct, the sponsor will also provide additional written guidance, if needed.

Considerations for Making a Change

The prevailing consideration for making a change is ensuring the safety of study participants. Additional important considerations for making a change are compliance with Good Clinical Practice, enabling participants to continue safely in the study and maintaining the integrity of the study.

Informed Consent

Additional consent/assent from the participant will be obtained, as applicable, and/or as required by Ethical Review Boards and local regulations. Assent will also be obtained to the same parameters, with consent for participants reaching the legal age for consent during the trial for continued participation, for:

- participation in remote visits, as defined in Section "Remote Visits,"
- a change in the location of study intervention administration,

- alternate delivery of ancillary supplies, and
- provision of their personal or medical information required prior to implementation of these activities.

Changes in Study Conduct During Exceptional Circumstances

Changes in study conduct not described in this appendix, or not consistent with applicable local regulations, are not allowed. The following changes in study conduct will not be considered protocol deviations.

1. Remote Visits

In source documents and the CRF, the study site should capture the visit location and method, with a specific explanation for any data missing because of missed in-person site visits.

Telemedicine: Telephone or technology-assisted virtual visits, or both, are acceptable to complete appropriate assessments. Assessments to be completed in this manner include, but are not limited to,

- Immunization record
- AEs and product complaints
- Concomitant medications
- Clinician reported measures except for those assessments or fields that require joint manipulation, such as Joint Assessment, Enthesitis Assessment, Dactylitic Count, Physician's Global Assessment of Disease Activity, and Clinical Sacroiliitis
- Participant/Parent administered measures

Other alternative locations: Other procedures that may be done at an alternate location in exceptional circumstances are local draw labs, investigational product preparation and administration. This alternative location may count as an “on-site” visit with regard to the guidance in this appendix.

In the event that access to the site is not possible, and with approval from Lilly Medical, sites will follow the guidance in the table below.

Visit(s)	Guidance
V1-V2	If one of these visits cannot be accomplished at the site, then the visit should be postponed. Refer to Section “Screening Period Guidance” in this appendix for further screening guideline and Section “Adjustments to Visit Windows” in this appendix for visit window adjustments.
V7	This visit must be performed at site (Primary Outcome).

	Participants under Ixekizumab Arm	Participants under Adalimumab Arm
OLT Visits (V3-V6)	Use a combination of telephone/telemedicine with use of an acceptable alternative site for the safe administration of the ixekizumab injection and assessments performed by site personnel.	Use a combination of telephone/telemedicine with use of an acceptable alternative site for assessments performed by site personnel.
OLE Visits: V8, V11, V14, V17, V20, V23, V26, V29	Use a combination of telephone/telemedicine with use of an acceptable alternative site to perform the assessments required to be done by health care professional, and for the preparation and safe administration of the ixekizumab injection.	Use a combination of telephone/telemedicine with use of an acceptable alternative site to perform the assessments required to be done by health care professional and the delivery of treatment supplies for the actual visit and for the next 2 treatment-only visits (e.g., V8 + V9, V10).
Tx only visits: V9, V10, V12, V13, V15, V16, V18, V19, V21, V22, V24, V25, V27, V28	Use a combination of telephone/telemedicine for follow up with use of an acceptable alternative site for the safe administration of the injection for participants under ixekizumab treatment arm.	Telephone/telemedicine for follow up. Participants would have received additional treatment supplies in the previous regular visit.
LTE Visits: V30, V31,	Use a combination of telephone/telemedicine with use of an acceptable alternative site to	Use a combination of telephone/telemedicine with use of an acceptable alternative site to perform the

Visit(s)	Guidance	
V33, V36, V39, V42,V45, V48, V51, V54, V57, V60, V63, V66, V69	perform the assessments required to be done by health care professionals, and for the preparation and safe administration of the ixekizumab injection.	assessments required to be done by health care professionals and the delivery of treatment supplies for the actual visit and for the next 2 treatment-only visits (e.g., V31 + V32, V34).
LTE Tx Visits Only: V32, V34, V35, V37, V38, V40, V41, V43, V44, V46, V47, V49, V50, V52, V53, V55, V56, V58, V59, V61, V62, V64, V65, V67, V68		Telephone/telemedicine for follow up. Participants would have received additional treatment supplies in the previous regular visit.
ETV	Sites may use telephone/telemedicine.	Sites may use telephone/telemedicine.
Follow-up (V801-V803)	Telephone/telemedicine or use of an acceptable alternative site.	Telephone/telemedicine or use of an acceptable alternative site.

Abbreviations: ETV = early termination visit; LTE = long-term extension; OLE = open-label extension; OLT = open-label treatment; Tx = treatment; V = visit.

Any required procedures that cannot be conducted at that time should be conducted as soon as possible thereafter, using an unscheduled visit if necessary.

Regardless of the type of remote visits implemented, the protocol requirements regarding the reporting of AEs, SAEs, and product complaints remain unchanged. Furthermore, every effort should be made to enable participants to return to on-site visits as soon as reasonably possible, while ensuring the safety of both the participants and the site staff.

2. Local Laboratory Testing Option

Preferred collection of labs is centrally, but if the participant is unable to attend the site, labs can be collected locally in lieu of central laboratory testing. For participants unable to access investigator sites, laboratory testing will be conducted locally approximately every 8 weeks through Week 16, and then approximately every 12 weeks. Failure to have labs collected within the described ranges above will result in participant termination from the study. The local laboratory must be qualified in accordance with applicable local regulations.

When collecting local labs, sites should store/retain records from the labs including results, address, certification (College of American Pathologists/Clinical Laboratory Improvement Amendments [CAP/CLIA]) status, and reference ranges. The principal investigator/subinvestigator should document, sign, and date review of local labs per normal process and follow-up with the participant as needed. Local labs may be sent to the participant as this is standard process in clinical care.

These laboratory measures listed below are the minimum required to monitor participant safety and determine temporary or permanent discontinuation of investigational product. Additionally, investigators should include any symptom-based laboratory testing based on their interactions with their participants. As stated in the protocol, investigators are responsible for monitoring the overall health of their participants.

Because these participants have already successfully screened into the study (therefore have met all study inclusion/exclusion criteria for laboratory values), the investigators should request the following laboratory analyses for these select parameters:

- 1) ALT, AST, total bilirubin, INR
- 2) ALP
- 3) WBC
- 4) Neutrophil and lymphocyte count
- 5) hemoglobin
- 6) platelet count
- 7) Serum pregnancy tests (where applicable)

Notes:

Serum pregnancy is to ensure female participants do not become pregnant while participating in the study (in lieu of urine pregnancy testing at the study site).

Temporary interruption rules (see Protocol RHCG Section 8.1.2) must be followed where applicable. For laboratory values that meet permanent discontinuation thresholds, investigational product should be discontinued. However, if in the opinion of the investigator the laboratory abnormality is due to intercurrent illness such as cholelithiasis or another identified factor, laboratory tests may be repeated. Only when

the laboratory value meets resumption thresholds following the resolution of the intercurrent illness or other identified factor may the investigator restart investigational product after consultation with Lilly Medical.

In some circumstances, participants may need to temporarily interrupt treatment as a result of AEs or abnormal laboratory values that may have an unclear relationship to investigational product. See Protocol RHCG Section [9.4.5](#) for details regarding managing participants who test positive for TB at any time during the study.

3. Study Intervention and Ancillary Supplies

When a participant is unable to go to the site to receive study supplies during normal on-site visits, the site should work with the sponsor to determine appropriate actions. These actions may include:

- asking the participant to go to the site and either receive study supplies or have injection administration from site staff without completion of a full visit,
- arranging delivery of study supplies, and
- working with the sponsor to determine how study intervention that is typically administered on-site will be administered to the participant at an alternate location.

These requirements must be met before action is taken:

- Alternate delivery of study intervention should be performed in a manner that ensures product integrity. The existing protocol requirements for product accountability remain unchanged, including verification of study supplies.
- When delivering supplies to a location other than the study site as an alternative site for the safe administration of the ixekizumab injection or the supply treatment for adalimumab. The investigator, sponsor, or both should ensure oversight of the shipping process to ensure accountability and product quality (that is, storage conditions maintained and intact packaging upon receipt).
- Instructions may be provided to the participant or designee on the final disposition of any unused or completed study supplies.

In addition, if study intervention will be administered to the participant at an alternate location, these additional requirements must be met:

- Only authorized study personnel may supply, prepare, or administer study intervention.
- Requirements and instructions for investigational product storage and dose preparation will be the same as stated in main protocol,

Pharmacy Binder and Ixekizumab Dosing Instructions Manual must be followed.

4. Screening Period Guidance

To ensure safety of study participants, laboratory values, and other eligibility assessments taken at screening visit are valid for a maximum of 42 days. The following rules will be applied for active, nonrandomized participants whose participation in the study must be paused due to exceptional circumstances:

- If paused for less than 42 days from screening to randomization visit: The participant will proceed to the next study visit per the usual Schedule of Activities, provided that randomization visit must be conducted within 7 days from first screening.
 - The site should conduct the next visit if the participant's eligibility criteria are confirmed, and the site should document the reason for delay in the CRF.
 - Due to the pause in screening, sites should also reconfirm the impacted participant's consent and document this confirmation in the source documentation.
- If paused for more than 42 days from screening to randomization visit: The participant must be discontinued because of screening interruption due to an exceptional circumstance. This is documented as a screen fail in the CRF with a reason of exceptional circumstance. This screen fail is allowed in addition to the main protocol screen fail. The participant can reconsent and be rescreened as a new participant. The screening procedures per the usual Schedule of Activities should be followed, starting at screening visit to ensure participant eligibility by randomization visit.

5. Adjustments to Visit Windows

Whenever possible and safe to do so, as determined by the investigator's discretion, participants should complete the usual Schedule of Activities. To maximize the possibility that these visits can be conducted as on-site visits, the windows for visits may be adjusted, upon further guidance from the sponsor. This minimizes missing data and preserves the intended conduct of the study.

This table describes the allowed adjustments to visit windows.

Visit Number	Tolerance
Visit 3 through Visit 7 (OLT)	Within 14 days before intended date, or up to 14 days after the intended date

Visit 8 through Visit 29 (OLE)	Within 14 days before intended date, or up to 14 days after the intended date
Visit 30 through Visit 69 (LTE)	Within 14 days before intended date, or up to 14 days after the intended date
Visit 801 through Visit 802 (Visit 803)	Within 14 days before intended date, or up to 14 days after the intended date

Abbreviations: LTE = long-term extension; OLE = open-label extension; OLT = open-label treatment.

For participants whose visits have extended windows, additional study intervention may need to be provided to avoid interruption and maintain overall integrity of the study, as well as to prevent dosing administration less than 21 days apart.

Documentation

Changes to study conduct will be documented:

- Sites will identify and document the details of how participants, visits types, and conducted activities were affected by exceptional circumstances.
- Dispensing/shipment records of study intervention and relevant communications, including delegation, should be filed with site study records.
- Source documents generated at a location other than the study site should be part of the investigator's source documentation and should be transferred to the site in a secure and timely manner.

